5.6.3 Disposition of subjects (Table 14.1-1 – 14.1-2)

5.6.3.1 The number of subjects that randomized into the study, the number of subjects in the ITT, mITT and PK populations, and the number of study completers will be presented.

5.6.3.2 The reasons for early termination/ withdrawal and any randomization errors will be summarized.

5.6.4 Demographic and Baseline data (Tables 14.1-3 -14.1-6)

5.6.4.1 Baseline and demographic data will be summarized in appropriate tables by treatment group and overall using the ITT population. These data includes demographic characteristics (age, gender, ethnicity and race), weight, height, BMI, medical history and disease-related information.

	DOCUMENT NUMBER: 029-BST-PLN-001	PAGE: 30 of 45
TITLE: Statistical Analysis Plan for study: A Phase 2 Randomized, Double-Blind, Placebo-Controlled, Parallel-Cohort Study to Evaluate the Efficacy, Safety, Tolerability, and Pharmacokinetics of Once-Daily Application of Topical VDA-1102 Ointment for 28 Days in Subjects with Actinic Keratosis	EFFECTIVE DATE : 22/MAY/2017 REVISION NUMBER : 2.0	

## 5.6.5 Efficacy Primary Analysis

- 5.6.5.1 The efficacy analysis will be performed with the ITT, mITT and PP populations (see Tables 14.2-1 - 14.2-9). The primary efficacy endpoint is the decrease from baseline in number of AK lesions. The within-group decrease in number of AK lesions from baseline to each visit will be analyzed using paired t-test or signed rank test for two means (paired observations, as is appropriate).
- 5.6.5.2 Comparative analysis of the decrease at Day 56 (mentioned above) will be applied between each of the active groups versus the placebo group using the two-sample t-test, the non-parametric Wilcoxon-Mann-Whitney rank sum test for independent samples, or the Median test (as appropriate) and using the Analysis of Covariance (ANCOVA), after optionally ranking transformation of the variable, with adjustment for sites and for other covariates suspected as affecting the outcome and which will be found different between the treatment groups.
- 5.6.5.3 Figures depicting the number of lesions by visit and by treatment group and depicting the reduction in number of lesions from Baseline to Day 56 will be generated
- 5.6.5.4 Binary variable will be defined based on the decrease in number of AK lesions at Day 56 according to a relevant cutoff (first quartile, median, third quartile or other cutoff computed by ROC curve sensitivity analysis). Comparative analysis of this variable will be applied between each of the active groups versus the placebo group using Chi-square test or Fisher's Exact test and using logistic regression with adjustment for site and for other covariates suspected as affecting the outcome and which will be found different between the treatment groups.

	DOCUMENT NUMBER: 029-BST-PLN-001	PAGE: 31 of 45
TITLE: Statistical Analysis Plan for study:  A Phase 2 Randomized, Double-Blind, Placebo-Controlled, Parallel-Cohort Study to Evaluate the Efficacy, Safety, Tolerability, and Pharmacokinetics of Once-Daily Application of Topical VDA-1102 Ointment for 28 Days in Subjects with Actinic Keratosis	EFFECTIVE DATE : 22/MAY/2017 REVISION NUMBER : 2.0	

5.6.5.5 If the two active VDA-1102 groups trend similarly then these two groups may be pooled and compared to the placebo group in order to achieve higher statistical power.

5.6.5.6 The overall effect and trend of differences in the decrease over time between the groups will be analyzed using a mixed-effect model for repeated measures. The model will include decrease from baseline at any time, the fixed effect time, and the interaction of treatment and time. Contrast will be calculated for each time point (Days 7, 14, 28 and 56) versus baseline and the overall effect. The model will be adjusted for site and for other covariates suspected as affecting the outcome and which will be found different between the treatment groups.

5.6.5.7 For the ANCOVA analysis, logistic regression and mixed-effect model for repeated measures detailed above, if necessary, grouping of sites will be done based on similarities and differences observed between sites by post-hoc contrasts of ANOVA.

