### **Statistical Analyses:**

#### ***Efficacy Analysis***

Efficacy analysis will be based on changes from baseline to Day 56 in AK lesions. Comparative analysis of the changes will be applied between each of the active groups versus the placebo group using the two-sample t-test or non-parametric Wilcoxon-Mann-Whitney rank sum test for independent samples or Median test (as is appropriate). In the event that the number of baseline lesions is different between the treatment groups, then relative changes (%) will be analyzed as well.

The overall change and the trend of differences in the changes over time between the groups will be analyzed using mixed-effect model for repeated measures. The model will include changes at any time, the fixed effect time and the interaction of treatment and time. The model will be adjusted for baseline measures and for other relevant covariates.

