#### 17.2.1 Efficacy Analysis

The efficacy analysis will be performed with the ITT, mITT, and PP populations (see Section 17.5.2). The primary efficacy endpoint is the change from baseline in number of AK lesions. If the baseline lesions number will be found different between the treatment groups, then relative change (%) will be analyzed as well. The within-group absolute changes (decrease) in AK number of lesions from baseline to each visit will be analyzed using paired t-test or signed rank test for two means (paired observations, as is appropriate).

Comparative analysis of the above changes will be applied between each of the active groups versus the placebo group using the two-sample t-test, the non-parametric Wilcoxon-Mann-Whitney rank sum test for independent samples, or the Median test (as appropriate).

If no statistically significant differences are observed between the two active VDA-1102 groups then these two groups will be pooled and compared to the placebo group in order to achieve higher statistical power.

The overall effect and trend of differences in the changes over time between the groups will be analyzed using a mixed-effect model for repeated measures. The model will include changes from baseline at any time, the fixed effect time, and the interaction of treatment and time. Contrast will be calculated for each time point (Days 7, 14, 28, 35 and 56) versus baseline and the overall effect. The model will be adjusted for baseline measure and for other covariates suspected as affecting the outcome and which will be found different between the treatment groups.

In case the baseline number of lesions differs between the groups, analysis of relative change (%) will be applied as well.

Chi-square test or Fisher's exact test (as is appropriate) will be used for analyzing the difference in percent of subjects with complete clearance of study AK lesions at the end of the treatment. Logistic regression will be applied for analyzing the difference in proportions with adjustment for baseline measure and for other covariates suspected as affecting the outcome and which will be found different between the treatment groups.

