### **17.2.4 Exploratory Endpoints Assessment**

Chi-square test or Fisher's exact test (as is appropriate) will be used for analyzing the difference in percent of subjects with complete clearance of study AK lesions at the end of the treatment. Logistic regression will be applied for analyzing the difference in proportions with adjustment for baseline measure and for other covariates suspected as affecting the outcome and which will be found different between the treatment groups.

Sensitivity analysis will be applied for identifying the cut-off of the change (or relative change) from baseline in number of lesions on Day 56. Analysis of the difference in the binary change will be applied using Chi-square test or Fisher's exact test. Logistic regression will be applied for analyzing these differences with adjustment for baseline measure and for other covariates suspected of affecting the outcome and which will be found different between the treatment groups.

Additional exploratory endpoint assessments will be described in the Statistical Analysis Plan.

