## 5.6 Statistical Analysis

### 5.6.1 General

5.6.1.1 All measured variables and derived parameters will be listed individually and, if appropriate, tabulated by descriptive statistics. For categorical variables summary tables will be provided giving sample size, absolute and relative frequency and 95% CI (Confidence Interval) for proportions (if appropriate) by treatment group. For continuous variables summary tables will be provided giving sample size, arithmetic mean, standard deviation, coefficient of variation CV% (if appropriate), median, minimum and maximum and 95% CI (Confidence Interval) for means of variables (if appropriate) by treatment group. The data will be analyzed using the SAS ® version 9.3 or higher (SAS Institute, Cary North Carolina). Analyses presented in the clinical report but not mentioned in the SAP are unplanned or ad-hoc analyses.

5.6.1.2 Statistical methods presented in the SAP may be slightly different from those that are presented in the protocol. Differences are clearly stated in this SAP which supersedes the protocol only with regard to the way data will be handled and analysed.

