5.6.6.1.1 The number of grade  $\geq 2$  lesions

5.6.6.1.2 An adjusted number of lesions weighted by grade. The weighted grade will be computed as follows: (Number of grade I lesions) + (2  $\times$  Number of grade II lesions) + (3  $\times$  Number of grade III lesions).

5.6.6.2 Comparative analysis of the decrease in number of grade  $\geq 2$  lesions will be applied on a sub-group of subjects with at least one grade  $\geq 2$  lesion at baseline.

5.6.6.3 Figures displaying the reduction in number of grade  $\geq 2$  lesions and the reduction of adjusted number of lesions weighted by grade from Baseline to Day 56 will be generated.

	DOCUMENT NUMBER: 029-BST-PLN-001	PAGE: 32 of 45
TITLE: Statistical Analysis Plan for study:  A Phase 2 Randomized, Double-Blind, Placebo-Controlled, Parallel-Cohort Study to Evaluate the Efficacy, Safety, Tolerability, and Pharmacokinetics of Once-Daily Application of Topical VDA-1102 Ointment for 28 Days in Subjects with Actinic Keratosis	EFFECTIVE DATE : 22/MAY/2017 REVISION NUMBER : 2.0	

5.6.6.4 Chi-square test or Fisher's exact test (as is appropriate) will be used for analyzing the difference in percent of subjects with complete clearance of study AK lesions at Day 56 between each of the active groups versus the placebo group. Logistic regression will be applied for analyzing the difference in proportions of complete clearance with adjustment for site and for other covariates suspected as affecting the outcome and which will be found different between the treatment groups.

5.6.6.5 All analyses mentioned above on complete clearance will be performed on  $\geq 75\%$  clearance,  $\geq 50\%$  clearance and  $\geq$  overall median% clearance as well.

5.6.6.6 Analyses mentioned above on complete clearance will be performed on clearance of grade  $\geq 2$  lesions as well.

5.6.6.7 The within-group decrease in number of AK lesions from baseline to each visit will be analyzed using paired t-test or signed rank test for two means (paired observations, as is appropriate) on the Day 84 completers subgroup.

5.6.6.8 Comparative analysis of the decrease in number of AK lesions from baseline to day 84 will be applied between each of the active groups versus the placebo group using the two-sample t-test, the non-parametric Wilcoxon-Mann-Whitney rank sum test for independent samples, or the Median test (as appropriate).

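### The SAP puts site where the protocol had baseline lesion count in the mixed and logistic models, leaves baseline out of its new Day 56 ANCOVA, and does not declare the change

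*SAP*

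**What the plan says.** **Protocol.** For the mixed model the synopsis says "The model will be adjusted for baseline measures and for other relevant covariates", with no condition about balance. Section 17.2.1 says "The model will be adjusted for baseline measure and for other covariates suspected as affecting the outcome", and then limits those other covariates to ones on which the arms differ. For the logistic models, sections 17.2.1 and 17.2.4 describe "analyzing the difference in proportions with adjustment for baseline measure and for other covariates suspected as affecting the outcome". The protocol contains no ANCOVA. Its between-arm comparison is a t-test, Wilcoxon or Median test without covariates.

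**SAP.** The Day 56 ANCOVA in 5.6.5.2 is specified "with adjustment for sites and for other covariates suspected as affecting the outcome and which will be found different between the treatment groups". For the mixed model, 5.6.5.6 says "The model will be adjusted for site and for other covariates suspected as affecting the outcome". The logistic model for the binary decrease (5.6.5.4) names site in the same way, and the clearance model (5.6.6.4) describes "analyzing the difference in proportions of complete clearance with adjustment for site and for other covariates suspected as affecting the outcome". Section 5.6.5.7 adds that, if needed, "grouping of sites will be done based on similarities and differences observed between sites by post-hoc contrasts of ANOVA". Baseline is defined in 5.6.2.1.1, but no efficacy model names it.

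**On departures from the protocol**, SAP 5.6.1.2 says: "Differences are clearly stated in this SAP which supersedes the protocol only with regard to the way data will be handled and analysed".

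**The concern.** Subjects enter with 4 to 8 lesions, so the starting count limits how many lesions a subject can lose. Randomization balances the arms overall and within the PK sub-cohort, not per site (SAP 5.2.5.2), and no balancing on lesion count is described. The protocol dealt with this by naming baseline in its models in advance.

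Under the SAP, baseline is one of the other covariates and enters only if the arms are judged to differ on it. No test or cut-off is given, so the content of the model depends on the data. Checking for imbalance also misses the main reason to adjust, which is to remove outcome variance that baseline explains even when the arms are balanced.

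Because 5.6.1.2 promises that departures are stated, a reader who relies on it would not learn that the adjustment set had changed.

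**Working it through.** **1. Side-by-side reading**

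| Model | Protocol: named covariate | SAP: named covariate |
|---|---|---|
| Mixed model | Baseline (synopsis, 17.2.1) | Site (5.6.5.6) |
| Logistic, binary decrease at Day 56 | Baseline (17.2.4) | Site (5.6.5.4) |
| Logistic, complete clearance | Baseline (17.2.1, 17.2.4) | Site (5.6.6.4) |
| Day 56 ANCOVA | Not in the protocol | Sites (5.6.5.2) |

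The substitution is consistent across all three shared models, and no SAP section mentions it.

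**2. The plan's own figure**

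Inputs (protocol 17.1, SAP 5.3.2): effect size 0.83, two-sided alpha 0.045, 25 per arm. The noncentrality is 0.83 × √(25/2) = 2.93 on 48 degrees of freedom, with a critical value of 2.06. Power is 80.7%, so the stated 80% is reproduced.

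**3. A plausible correlation r between baseline count and decrease**

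The documents do not give r. Assume counts uniform on 4 to 8 (mean 6, variance 2, mean square 38) and per-subject clearance probability Beta with mean m and a+b = s. Then:

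- Var(decrease) = 2m² + m(1−m)(6s + 38)/(s + 1)
- r = m√2 / √Var(decrease)

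| m | s | Var(decrease) | r |
|---|---|---|---|
| 0.25 | 2 | 0.125 + 3.125 = 3.25 | 0.196 |
| 0.25 | 4 | 0.125 + 2.325 = 2.45 | 0.226 |
| 0.50 | 2 | 0.5 + 4.167 = 4.667 | 0.327 |
| 0.50 | 4 | 0.5 + 3.1 = 3.6 | 0.373 |

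The working range is therefore r = 0.20 to 0.37.

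**4. Power of the Day 56 ANCOVA with and without baseline**

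Assumptions: pairwise model, 25 per arm, sites allocated at random and not prognostic. Residual SD is multiplied by √(1−r²). Noncentral-t power is averaged over 5,000 random designs, so chance site-by-arm imbalance is included.

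| Site terms | Without baseline | r=0 | r=0.2 | r=0.3 | r=0.37 |
|---|---|---|---|---|---|
| None | 80.7 | 79.8 | 81.4 | 83.5 | 85.4 |
| 3 groups | 78.9 | 78.0 | 79.7 | 81.7 | 83.7 |
| 9 sites | 72.7 | 71.6 | 73.3 | 75.6 | 77.8 |

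With site in the model, adding baseline gains 0.6 points (9 sites, r=0.2) to 5.1 points (9 sites, r=0.37). At r=0 it loses 0.9 (3 groups) to about 1.2 points (9 sites). The standard error is multiplied by 0.99 at r=0.2 and 0.94 at r=0.37. Most of the fall from 80.7% to about 73% comes from fitting nine sites, not from omitting baseline.

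**5. Does the conditional rule recover the gain?**

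Assume the trigger is a baseline difference at p<0.05, with no site terms. Simulated power for never / always / conditionally adjusted is 80.7 / 83.5 / 80.9% at r=0.3 and 80.8 / 85.5 / 81.0% at r=0.37. It recovers very little. Its type I error stays within the nominal 4.5% (4.3% at r=0.3).

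**6. Logistic models**

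Under the step 3 assumptions, expected complete clearances per 25 subjects are 0.88 and 0.36 (m=0.25, s=2 and 4) and 3.73 and 2.27 (m=0.5). That is too few for a power claim. With clearance 0.25 against 0.5 and 50 subjects, the complete-clearance model with baseline separates in 100% of trials with nine sites, 70–89% with three groups, and 44–76% with no site term. The nine-site model without baseline already separates in 100%, so the site term is the cause. An arm has no events in 42–72% of trials.

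**The case against.** The strongest case against is that the quantified loss falls on a model the protocol never had. The ANCOVA is an SAP addition, so no planned adjustment was removed there. For the mixed model, where adjustment was removed, no figure is derived, and for the logistic models no power claim is made. The powered comparison and its 80% are untouched, no false-positive risk is shown, and r rests on assumptions. This stands, and it limits how serious the point is.

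The figures also depend on model form. The SAP's table list has a single Day 56 ANCOVA table, which may mean one three-arm model. With 75 subjects and nine sites that model has 76.3% power rather than 72.7%, and the cost at r=0 is about 0.6 to 0.7 points. The gain is still about 1 to 5 points, so the conclusion does not change. The SAP also allows a rank transformation, which these figures do not cover.

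Protocol 17.2.1 could be read as making baseline conditional too. The synopsis wording favours the unconditional reading.

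Relative-change tables and percent-clearance endpoints scale to the starting count, which helps, but that is not covariate adjustment. The detailed table shells are in a separate document and might name covariates. That would not supply the missing declaration in the SAP.

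**Conclusion.** The concern holds. The replacement of baseline by site in the mixed and logistic models, and its absence from the ANCOVA, are matters of text and need no assumption. So is the failure to declare the change.

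The statistical consequence is modest. Baseline adjustment is worth about 0.6 to 5 points of power in the site-adjusted Day 56 ANCOVA. This assumes r between 0.20 and 0.37, 25 per arm and non-prognostic sites. The clause admitting baseline only when the arms differ covers part of the chance-imbalance problem and almost none of the precision. The primary unadjusted tests and the sample size are not affected.

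**What to change.** 1. In SAP 5.6.5.2 and 5.6.5.6, name baseline AK lesion count (as defined in 5.6.2.1.1) as a fixed covariate alongside site, whatever the observed balance.
2. In the logistic models (5.6.5.4, 5.6.6.4), restore baseline as the protocol's fixed covariate. Keep site only where event counts support it, grouped or dropped by a rule set in advance and not by the outcome-based contrasts of 5.6.5.7.
3. Where an arm has no events, report the Fisher test already planned in 5.6.6.4 in place of the logistic model. Also say what is reported if the fit separates with events in both arms.
4. Under 5.6.1.2, record that site was added relative to protocol 17.2.1 and 17.2.4, and that the ANCOVA is new.

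**Cost.** SAP wording only, with no new data. Baseline takes one degree of freedom in the ANCOVA and the mixed model. In the pairwise ANCOVA that is 0.9 to 1.2 points of power if baseline is unrelated to the decrease. Site may have to be dropped from the complete-clearance logistic model, which would lose site adjustment there.

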#### 5.6.6 Exploratory Analysis

5.6.6.1 Two new variables will be defined and all comparative analyses that were done for the primary analysis above will be repeated for these two new variables:

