## 9. APPENDICES

### APPENDIX I: TABLE SHELLS

Table 14.1-1: Subject Disposition  
 Table 14.1-2: Demographic Data  
 Table 14.1-3: Frequency of Medical History (except Actinic Keratosis) by Category  
 Table 14.1-4: Any Medications within 30 Days Prior to Screening  
 Table 14.1-5: Any Medications between Screening and Day 1 Dosing Visit  
 Table 14.1-6: Disease-related information  
 Table 14.1-7: Dermatological Evaluation at Pre-dose  
 Table 14.1-8: Compliance Data

Table 14.2-1: AK Lesions Count in ITT Population  
 Figure 14.2-1: Total Number of Lesions by Visit and by Study Group in ITT Population  
 Figure 14.2-2: Number of AK Grade  $\geq 2$  lesions by Visit and by Study Group in ITT Population  
 Figure 14.2-3: Adjusted Number of Lesions by Visit and by Study Group in ITT Population

Table 14.2-2: AK Lesions Count in mITT Population  
 Table 14.2-3: AK Lesions Count in PP Population  
 Table 14.2-4: AK Lesions Number: Absolute Changes from Baseline in ITT Population  
 Table 14.2-5: AK Lesions Number: Changes from Baseline in mITT Population  
 Table 14.2-6: AK Lesions Number: Changes from Baseline in PP Population  
 Table 14.2-8: AK Lesions Number: Changes from Baseline for Day 84 Completers

Table 14.2-9: AK Lesions Number: Relative Changes from Baseline in ITT Population (%)  
 Table 14.2-10: AK Lesions Number: Relative Changes from Baseline in mITT Population (%)  
 Table 14.2-11: AK Lesions Number: Relative Changes from Baseline in PP Population (%)  
 Table 14.2-12: AK Lesions Number: Relative Change from Baseline for Day 84 Completers

Table 14.2-13: Frequency of Decrease in AK lesions at Day 56  $\geq$  Cutoff Computed by Sensitivity Analysis/ Relevant Quartile in ITT Population  
 Table 14.2-14: Frequency of Decrease in AK lesions at Day 56  $\geq$  Cutoff Computed by Sensitivity Analysis/ Relevant Quartile in mITT Population  
 Table 14.2-15: Frequency of Decrease in AK lesions at Day 56  $\geq$  Cutoff Computed by Sensitivity Analysis/ Relevant Quartile in PP Population

MediStat Statistics in Medicine	DOCUMENT NUMBER: 029-BST-PLN-001	PAGE: 42 of 45
TITLE: Statistical Analysis Plan for study: A Phase 2 Randomized, Double-Blind, Placebo-Controlled, Parallel-Cohort Study to Evaluate the Efficacy, Safety, Tolerability, and Pharmacokinetics of Once-Daily Application of Topical VDA-1102 Ointment for 28 Days in Subjects with Actinic Keratosis	EFFECTIVE DATE : 22/MAY/2017 REVISION NUMBER : 2.0	

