Table 14.2-16: AK Lesions Number: Change in Number of AK Grade  $\geq 2$  Lesions on Patients with at least one Grade  $\geq 2$  Lesion at Baseline (ITT Population)

Table 14.2-17: AK Lesions Clearance (ITT Population)

Table 14.2-18: AK Grade  $\geq 2$  Lesions Clearance (ITT Population)

Table 14.2-19: ANCOVA Model at Day 56 (ITT Population)

Table 14.2-20: Mixed Model for Repeated Measures (ITT Population)

Table 14.2-21: Logistic Model for Change in Total Number of Lesions  $\geq$  cutoff XX at Day 56 (ITT Population)

Table 14.2-22: Logistic Model for Change in Number of AK Grade  $\geq 2$  lesions  $\geq$  cutoff XX (ITT Population)

Table 14.2-23: Logistic Model for Change in Adjusted Number of Lesions Weighted by Grade (ITT Population)

Table 14.2-25: Logistic Model for Complete Clearance at Day 56 (ITT Population)

Table 14.2-26: Logistic Model for 75% Clearance at Day 56 (ITT Population)

Table 14.2-27: Logistic Model for 50% Clearance at Day 56 (ITT Population)

Table 14.2-28: Logistic Model for XX% Clearance at Day 56 (XX is the median of clearance percent in all patients ) (ITT Population)

Table 14.2.29 Summary of PK Parameters from VDA-1102

Table 14.2.31 Summary of PK Parameters from Jasmonic Acid

Table 14.3.1-1: Incidence of Adverse Events

Table 14.3.1-2: Summary of Adverse Events

Table 14.3.1-3: Summary of Adverse Events by Relationship to Study Medication

Table 14.3.1-4: Summary of Adverse Events by Severity

Table 14.3.1-5: Summary of Treatment Emergent Adverse Events

Table 14.3.1-6: Summary of Treatment Emergent Adverse Events by Relationship to Study Medication

Table 14.3.1-7: Summary of Treatment Emergent Adverse Events by Severity

Table 14.3.1-8: Summary of Treatment Emergent Serious Adverse Events

Table 14.3.5-1: Summary Statistics of Hematology Results

Table 14.3.5-2: Summary Statistics of Hematology Change from Baseline

Table 14.3.5-3: Summary Statistics of Chemistry Results

Table 14.3.5-4: Summary Statistics of Chemistry Changes from Baseline

Table 14.3.5-5: Summary Statistics of Coagulation Results

Table 14.3.5-6: Summary Statistics of Coagulation Change from Baseline

MediStat Statistics in Medicine	DOCUMENT NUMBER: 029-BST-PLN-001	PAGE: 43 of 45

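### SAP 5.6.5.4 lets the Day 56 responder cutoff be found by ROC on the trial's own data and then tested on those data, inside the primary analysis section

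*SAP*

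**What the plan says.** SAP 5.6.5 is headed as the primary efficacy analysis. Its item 5.6.5.4 begins "Binary variable will be defined based on the decrease in number of AK lesions at Day 56", and the split is made "according to a relevant cutoff (first quartile, median, third quartile or other cutoff computed by ROC curve sensitivity analysis". The new variable is then compared between each active group and placebo by chi-square or Fisher, and by logistic regression adjusted for site and other covariates.

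The table shells in SAP Appendix I leave the choice open. Tables 14.2-13 to 14.2-15 cover the ITT, mITT and PP populations; the first is titled in part "Cutoff Computed by Sensitivity Analysis/ Relevant Quartile in ITT Population". "Table 14.2-21: Logistic Model for Change in Total Number of Lesions" carries the placeholder XX where the cutoff should stand.

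Protocol 17.2.4, on exploratory endpoints, plans the same step: "Sensitivity analysis will be applied for identifying the cut-off of the change (or relative change) from baseline in number of lesions on Day 56". It follows with the same kinds of test. SAP 5.6.1.2 says of departures from the protocol: "Differences are clearly stated in this SAP which supersedes the protocol only with regard to the way data will be handled and analysed". Nothing in the SAP mentions that this analysis has moved from exploratory to primary. SAP 5.6.6.1, in the exploratory section, adds that "all comparative analyses that were done for the primary analysis above will be repeated for these two new variables": the count of lesions of grade 2 or higher, and the grade-weighted count.

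**The concern.** A p-value from chi-square, Fisher or logistic regression assumes that the definition of response was set without reference to the comparison being tested. An ROC search with treatment arm as the class breaks that assumption, because it picks the cutoff at which the arms differ most by some criterion and the ordinary test then ignores the search. The SAP does not say that arm is the class, but nothing in it excludes this, and it names no outside data from which a cutoff could come.

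What is at stake is a secondary reading of the trial. A responder result produced this way would sit in the primary section beside the valid lesion-count comparison and could be taken as support for it.

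**Working it through.** **Inputs from the documents.** Three arms at 1:1:1; 25 evaluable per arm, from about 84 recruited with 10% dropout; baseline count 4 to 8 lesions; final two-sided level 0.045 after 0.005 at the interim (SAP 5.3.1 and 5.3.2). The stated design reproduces: a two-sample t-test with 25 per group, effect size 0.83 and alpha 0.045 has 80.7% power against the stated 80%, and 75/0.9 = 83.3, rounded up to 84.

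**Why the search and the test overlap.** Let a and b be the numbers of responders among n = 25 on active and on placebo. The Youden index at a cutoff is J = (a - b)/25. The uncorrected chi-square is

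X2 = 2n(a - b)^2 / [(a + b)(2n - a - b)] = 50(a - b)^2 / [(a + b)(50 - a - b)].

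For 16 against 9 responders, X2 = 50 x 49 / (25 x 25) = 3.92, just past the 5% critical value of 3.84. Both J and X2 are driven by a - b, so picking the cutoff with the largest J comes close to picking the one with the largest test statistic.

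**Null simulation.** The documents give no ROC rule, class variable or outcome distribution, so these are assumptions:

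- Arm is the ROC class, there is no drug effect, and the level is nominal two-sided 5%.
- Baseline is uniform on 4-8, with binomial decreases.
- Per-lesion clearance probability follows one of six forms: Beta(1.2,2.2), Beta(1,4), Beta(2,2), Beta(0.6,0.9), constant 0.35, or Beta(1.2,2.2) with Poisson(0.6) new lesions. Mean decrease runs from 1.2 to 3.0 and SD from 1.3 to 2.2.
- Response means a decrease at or above the cutoff. The fixed comparator is the integer giving nearest to 50% responders.
- There were two runs of 20,000 trials per scenario; ranges cover both runs and all six distributions.

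False positives for one active-placebo comparison, 25 per arm:

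| Cutoff rule | Chi-square, total | Chi-square, favouring drug | Fisher, total |
|---|---|---|---|
| Youden, either direction | 14.4-20.2% | 7.1-10.2% | 6.1-9.1% |
| Ordinary Youden | 7.2-10.5% | 7.2-10.5% | 3.0-4.5% |
| Sensitivity x specificity | 5.8-7.6% | 5.1-7.2% | 2.7-3.8% |
| Closest to (0,1) | 5.0-6.5% | 4.7-6.4% | 2.3-3.2% |
| Fixed in advance | 5.7-6.5% | 2.8-3.3% | 2.5-3.2% |

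The Beta(1.2,2.2) case shows the ratios to a fixed cutoff. Favouring the drug: either-direction Youden 0.098/0.033 = 3.0, ordinary Youden 0.100/0.033 = 3.0, product 0.070/0.033 = 2.1, closest 0.060/0.033 = 1.8. In total: 0.188/0.065 = 2.9, 0.100/0.065 = 1.5, 0.076/0.065 = 1.2 and 0.062/0.065 = 0.95.

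**The estimate is biased too.** The median null odds ratio, active against placebo, is 1.6-2.1 under ordinary Youden, 1.2-1.4 under the product and closest rules, and 1.0 with a fixed cutoff.

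**Variations.**

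- *Either of two doses favouring the drug, chi-square:* ordinary Youden 12.7-17.9%, product 9.4-12.7%, closest 8.7-11.4%, fixed 5.1-5.8%.
- *28 per arm (the planned ITT size), favouring the drug:* ordinary Youden 6.1-9.1%, fixed 2.1-2.6%.
- *Level 0.045, either-direction Youden, a separate set of null distributions with 25 or 28 per arm:* 13.2-17.4% in total, against 4.2-5.0% fixed.
- *Class other than arm (complete clearance, arms pooled):* 3.0-5.7%, no inflation.
- *Quartiles:* at most 6.3% if one is fixed blind; 9.8-14.0% if all three are tested by arm and the best is kept.
- *Permutation test repeating the ordinary Youden search, one-sided 2.5%:* 1.4-1.6%, against 9.5-9.7% uncorrected.

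**The case against.** The inflation needs arm to be the ROC class, and neither document says so. With the one other class tried it vanishes, so strictly the text shows under-specification. That stands, and it limits the size of the claim. It does not clear the analysis, because the SAP as written permits the biased version.

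For two of the four rules the total error hardly moves: 0.85-1.04 times fixed for closest to (0,1), and 1.0-1.2 times for the product rule. Also correct. Under those rules the errors shift towards the drug, which is the direction that would mislead.

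Fisher, which the SAP allows, keeps three of the four rules below 5% in total. True, but its drug-favouring errors still rise: 3.0-4.5% under ordinary Youden against 1.3-1.6% with a fixed cutoff.

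The site-adjusted logistic regression was not simulated. Ties between integer cutoffs were common; in the Beta(1.2,2.2) case their handling moved ordinary Youden from 9.4% to 9.9%. The first is a gap; the second is small.

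Finally, the protocol already plans the same search and tests, so only the heading changed, and headings are used loosely: Protocol 17.2.1 also covers complete clearance, an exploratory endpoint. The named primary endpoint remains the change in lesion count, and no alpha is given to the responder variable. All of this is fair and is why the point is minor. Still, the SAP has its own exploratory section, says that differences from the protocol are stated, and does not state this one.

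**Conclusion.** The concern holds, as a minor point. That the cutoff is left open, and that its status changes between protocol and SAP without notice, follows from the text alone. The size is conditional. With arm as the ROC class, 25 per arm and the assumed outcome distributions, chi-square false positives favouring the drug run from 1.5 to 3.4 times those of a fixed cutoff, depending on the rule. Totals run from no increase to 3.4 times. With a class unrelated to arm, no inflation appeared. A single quartile fixed without sight of results by arm is acceptable. The primary endpoint and its test are untouched. Confidence is medium, because the rule, the class and the outcome distribution are not in the documents.

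**What to change.** 1. Move SAP 5.6.5.4 to section 5.6.6, matching Protocol 17.2.4, and label Tables 14.2-13 to 14.2-15 and 14.2-21 as exploratory.
2. Before unblinding, name one cutoff for each count variable, including the two repeats under 5.6.6.1. Alternatively, drop this analysis and rely on the thresholds already planned in 5.6.6.4 and 5.6.6.5: complete, at least 75% and at least 50% clearance.
3. If an ROC-derived cutoff is still wanted, report it descriptively only, or with a permutation p-value in which every permutation repeats the cutoff search. State the ROC rule and the class variable.

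The cost is SAP wording. No new data are needed and the primary test loses nothing. The one thing given up is quoting a data-optimised cutoff with an ordinary p-value.
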